17 18 19	15.3 Publi 16.1 16.2 Intell Repo 18.1 18.2 18.3 Histo Refer	Indemnity c and Patient Involvement The aims of active involvement in this project A description of the methods of involvement ectual Property rting, publications and notification of results Authorship policy Publication Ancillary studies rry of Amendments to Protocol	38 39 39 40 40 40 41 41 42 43
17 18 19 20	15.3 Publi 16.1 16.2 Intell Repo 18.1 18.2 18.3 Histo Refer Appe	Indemnity c and Patient Involvement The aims of active involvement in this project A description of the methods of involvement ectual Property rting, publications and notification of results Authorship policy Publication Ancillary studies rry of Amendments to Protocol	38 39 39 40 40 40 41 41 42 43 44

1 Trial summary

Title

High Or Low Dose Syntocinon® for delay in labour (HOLDS)

Settings

Obstetric departments in approximately 30 hospitals within the UK.

Trial Design

Multicentre, randomised, double blind controlled trial of 1500 nulliparous women with confirmed delay in labour and ruptured membranes.

Aims

Primary objective:

• To perform a robust multicentre, randomised, double blind controlled trial to evaluate the effect on CS rate of high dose regimen versus standard dose regimen oxytocin for nulliparous women at term (37-42 weeks gestation) with confirmed delay in the first stage of labour using NICE definitions.

Secondary objectives are to:

- To assess the effect on maternal and neonatal outcomes.
- To explore any variation in effect in women randomised with cervical dilation <6cms and >=6cms.
- To assess the safety of high dose oxytocin. Oxytocin can cause excess contractions (tachysystole) which can cause abnormalities of the fetal heart rate (hyperstimulation) and we will collect information regarding safety for both women and babies.

Target Population

Nulliparous women with a singleton cephalic pregnancy at term (37-42 weeks gestation) with confirmed delay in labour and ruptured membranes as defined by NICE Intrapartum Care Guideline [NICE 2014] for whom the clinical decision has been made to prescribe Syntocinon for augmentation of labour.

Health Technologies Assessed

Standard dose regimen of oxytocin (2mU/min increasing every 30 minutes to a maximum 32mU/min) compared with high dose regimen (4mU/min increasing every 30 minutes to a maximum of 64mU/min).

2 Lay Summary

We currently do not know the best care for first time mothers with delayed progress in the first stage of labour and this topic is a research priority for the Royal College of Obstetricians and Gynaecologists. Delayed labour is a relatively common occurrence affecting between 11- 30% (equivalent to between one and three in ten) of first time mothers becoming delayed in labour.

The only recommended treatment for women delayed in the first stage of labour is artificial oxytocin (Syntocinon®) which is given intravenously to stimulate contractions. A standard regimen (concentration and rate of administration) is recommended by NICE Guidelines 2014 and is widely used in the UK. Information from studies looking at different dose regimens of Syntocinon ® in delayed labour suggest that a high dose regimen may reduce the chance of Caesarean section but the available evidence is not conclusive. Syntocinon ® may cause the uterus to contract too much and the baby to become distressed so both mother and baby are carefully monitored and the dose adjusted in relation to the number of contractions and how the baby is.

Research shows currently around 32% (equivalent to about three in ten) of the women who need Syntocinon[®] for delayed labour have an unplanned Caesarean section , which we know is related to a longer hospital stay, higher risk of infection, bleeding and blood clots and to increase risk of Caesarean section in future pregnancies. By reducing Caesarean section we can reduce these risks to women. A reduction in the Caesarean section rate of 5-8% (equivalent to nearly one in ten) in these women could save the NHS nearly £1M per year, as well as possible annual savings of £2.6M from the impact of avoiding Caesarean section in future pregnancies.

Our proposed trial will randomise 1500 women to standard or high dose regimens of Syntocinon[®] and measure differences in rates of caesarean section as well as collecting information about the birth and safety of mother and baby. Clinicians will not be aware of which regimen of Syntocinon[®] is being given, and care will be the same for either group. Serious adverse events are more likely in this high risk group of women and these will be reviewed by an independent group (Data Monitoring Committee).

Recruiting women to clinical trials in labour is challenging, and in our pilot study we showed that informing all potentially eligible women about the study in late pregnancy, and approaching them during labour to discuss the study is acceptable. We have set a realistic target for recruitment of about 20% (equivalent to one in five) of eligible women, based on the pilot and realise the importance of training staff so they can explain the study and answer any questions women and their partners may have.

This application brings together a multidisciplinary team of experts-academics, clinicians, statisticians, and a service user, who together have successfully undertaken the pilot study. Information from this study will directly influence care of future women with delayed labour.

3 Contacts and Roles

3.1 Sponsor and Sponsor Roles

The Birmingham Women's NHS Foundation Trust (BWNFT) is the sponsor of HOLDS. The BWNFT is responsible for obtaining necessary approvals and for governance. The Trial Management Group is jointly responsible for overseeing good clinical practice and the Principal Investigators are responsible for obtaining informed consent and care of the participants.

3.5 Data Monitoring Committee

For interim analysis and response to specific concerns

- [name] (Chair), Consultant Obstetrician and Gynaecologist and Lead Obstetrician for Research Bradford Royal Infirmary, [name] [contact] Email: [contact]
- [name], Statistician National Perinatal Epidemiology Unit, [name] Email: [contact]
- [name], Senior Research Midwife Sonographer Insititute of Cellular Medicine, [name], The Newcastle upon Tyne Hospitals NHS Foundation Trust, [name] [contact] Email: [contact]

4 Abbreviations

AE	Adverse event
AR	Adverse reaction
ASR	Annual Safety Report
BCTU	Birmingham Clinical Trials Unit at the University of Birmingham
BWNFT	Birmingham Women's NHS Foundation Trust
CI	Chief Investigator
DMC	Data Monitoring Committee
GCP	Good Clinical Practice
GMP	Good Manufacturing Practice
GP	General Practitioner
ISRCTN	International Standard Randomised Controlled Trial Number
MREC	Multicentre Research Ethics Committee
PDF	Portable Document Format
PI	Principal Investigator – the local lead investigator
PIS	Participant Information Sheet
RR	Relative Risk
RSI	Reference Safety Information
SAE	Serious Adverse Event
SOP	Standard Operating Procedure
SPC	Summary of Product Characteristics
SUSAR	Suspected Unexpected Serious Adverse Reaction
TMG	Trial Management Group
TSC	Trial Steering Committee

5 Background

HOLDS Is a multicentre, randomised, double-blind randomised controlled trial to evaluate whether a high dose regimen oxytocin for nulliparous women delayed in the first stage of labour reduces the Caesarean section (CS) rate. These women have a relatively high rate of unplanned CS¹ (34%) and making sure the rate is as low as possible is important as unplanned CS is associated with longer stay in hospital, higher risk of infection, bleeding and blood clots and is associated with an increased risk of CS in subsequent pregnancies^{2,3,4}.

Robust evidence as to how best to care for women with delayed labour is lacking and it is a research priority for the Royal College of Obstetricians and Gynaecologists (RCOG). The length of labour for nulliparous women is on average 8 hours and it is unlikely to last over 18 hours⁵. In line with NICE guidance⁵ once a woman is in established labour (i.e. she has regular painful contractions and her cervix is 4cms or more dilated on examination) assessment of progress includes cervical dilation as well as descent and rotation of the baby's head and changes in the strength, duration and frequency of uterine contractions. Should delay be suspected (when cervical dilation of <2cm in four hours is found) the woman remains under the care of a midwife, providing all other parameters remain normal. During the two hour period until progress is re-assessed the midwife is likely to suggest interventions which would facilitate progress occurring. The midwife caring for the woman would encourage the woman to mobilise, consider hydration (e.g. a sports drink), and discuss appropriate and effective pain relief. If her membranes are still intact, artificial rupture (amniotomy) will also be advised. Once delay is confirmed if cervical progress < 1cm found on re-assessment, transfer to obstetric-led care would take place (if required) for an obstetric review and a decision about management options. The only recommended treatment is Syntocinon[®] which is an inexpensive licensed synthetic version of the hormone oxytocin. It is routinely given by intravenous infusion to stimulate contractions leading to birth.

5.1 Evidence for the dose regimen of oxytocin

The current standard regimen of oxytocin for confirmed delay⁶ suggests a starting dose of 1-2 mU/minute and increase intervals of 30 minutes or more to a maximum of 32mU/minute. This is given to increase the frequency and strength of uterine contractions with the aim that vaginal birth will be achieved. There is recent evidence from two systematic reviews that higher dose regimens (both of rate and strength) of oxytocin than currently recommended may decrease CS and increase vaginal birth rates, although there is insufficient evidence to recommend a change in practice.

The first review considered women delayed in normal labour (Cochrane Systematic Review⁷) comparing high versus low dose oxytocin regimens. The authors defined high dose oxytocin as a starting dose and increments >4mU/minute and low dose as a starting dose 1-4 mU/minute and increments of 1-2 mU/minute. The review included four trials and 644 women and showed a reduction in the risk of CS (RR 0.62; 95% CI 0.44 to 0.86) in favour of high dose regimen, although removing one trial at high risk of bias increased the uncertainty (RR: 0.89; 95%CI: 0.57 to 1.38; p=0.6). Even attempting to account for the heterogeneity using a random effects model which some would suggest was more appropriate⁸ resulted in an estimate that was not statistically significant (RR: 0.67; 95%CI: 0.38 to 1.18; p=0.2) (see Figure 1).

	High de	ose	Low de	ose		Risk Ratio	Risk Ratio
Study or Subgroup	Events	Total	Events	Total	Weight	M-H, Random, 95% Cl	M-H, Random, 95% Cl
Kenakis 1995	16	154	40	156	32.0%	0.41 [0.24, 0.69]	
Jamal 2004	5	100	9	100	17.5%	0.56 [0.19, 1.60]	
Bidgood 1987	5	19	7	21	19.4%	0.79 [0.30, 2.07]	
Kenyon 2013	17	47	15	47	31.0%	1.13 [0.64, 1.99]	
Fotal (95% CI)		320		324	100.0%	0.67 [0.38, 1.18]	•
Total events	43		71				

Similarly, there was no convincing evidence that a difference was seen in spontaneous vaginal birth rate due to doubts with the same trial and there were no differences noted in other outcomes: instrumental vaginal birth, epidural analgesia, hyper-stimulation, postpartum haemorrhage, chorioamnionitis or women's perceptions of experience.

The second review⁹ used similar definitions for oxytocin dose regimens (starting doses and increments of above and below 4mU/minute). Although results demonstrated high dose oxytocin regimens were associated with a reduction in the risk of CS this was in a mixed population. Ten randomised trials (5423 women) were included but seven of these were not trials which included women delayed in normal labour but trials of a package of care which included oxytocin called 'active management' of labour (one to one care in labour, strict definition of established labour, early routine amniotomy, routine two hourly vaginal examinations and oxytocin if labour becomes slow). No analysis was presented within the review to differentiate the reason for oxytocin being prescribed. The three trials included in which oxytocin was given for delayed normal labour (similar to the population in our proposed trial) are included in the Cochrane review above.

Further demonstration of the lack of conclusive evidence regarding routine use of a high dose regimen of oxytocin is seen in the NICE Guidance on Intrapartum Care⁵ which did not find sufficient evidence to warrant a review of the recommendation to use the standard dose regimen of oxytocin (2mU/min increasing every 30 minutes to a maximum 32mU/min) for women delayed in labour.

5.2 Additional relevant evidence

In the USA the Consortium of Safe Labor have recently published data that suggests that duration of labour appears longer today than in the past¹⁰ and that a cervical dilation of 6 cm appears to be a better marker for the start of the active phase of labour. This has been adopted by the American College of Obstetricians and Gynecologists with the Society for Maternal-Fetal Medicine in their consensus statement for 'Safe Prevention of Primary Caesarean Section'¹¹ as part of a number of strategies designed to reduce the caesarean section rate. In this statement they suggest that intervention for delayed labour should not start until the cervix is more than 6cms dilated and it is not clear what the standard oxytocin dose regimen should be. Using the data collected as part of the work undertaken by the Consortium of Safe Labor, an observational study¹² found no difference in CS rates with a so-called high dose oxytocin compared to a low dose. However, this study is open to methodological biases, the exact oxytocin dose regimens are unclear and, as they are presented within the paper, all the regimens would be considered standard dose regimens in the UK. Uptake of this evidence and the Consensus Statement¹¹ has been controversial in the USA¹³ and is unlikely to influence practice in the UK¹⁴. To ensure that the trial results will be of worldwide interest and relevance we will incorporate subgroup analysis of women commencing treatment less than 6cm and equal to or more than 6cm into our *a priori* statistical analysis plan.

6 Trial aim and objectives

6.1 Aim

HOLDS will provide robust evidence of clinical effectiveness of a high dose compared to the current standard dose regimen of oxytocin in reducing the need for Caesarean section (CS) for nulliparous women with confirmed delay in the first stage of labour.

6.2 Primary objective

• To perform a robust multicentre, randomised, double blind controlled trial to evaluate the effect on CS rate of high dose regimen versus standard dose regimen oxytocin for nulliparous women at term (37-42 weeks gestation) with confirmed delay in the first stage of labour using NICE definitions.

6.3 Secondary objectives

- To assess the effect on maternal and neonatal outcomes.
- To explore any variation in effect in women randomised with cervical dilation <6cms and >=6cms.
- To assess the safety of high dose oxytocin. Oxytocin can cause excess contractions (tachysystole) which can lead to abnormalities of the fetal heart rate (hyperstimulation) and we will collect information regarding safety for both women and babies.

7 Trial design

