7.3 Inclusion criteria

- Nulliparous women with singleton cephalic pregnancy at term (37-42 weeks gestation)
- Confirmed delay in labour and ruptured membranes for whom the clinical decision has been made to prescribe Syntocinon for augmentation of labour

According to NICE guidance [NICE 2014], labour is established when there are regular painful contractions and progressive cervical dilation from 4 cm. Delay is suspected when cervical dilation of

< 2 cm in 4 hours occurs once labour is established. Delay is confirmed when progress of <1 cm in 2 hours is found on repeat vaginal examination.

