7.8 Co-enrolment

Women participating in the HOLDS study cannot join other interventional trials of an IMP or procedure for delay in labour. They may be recruited to other intrapartum IMP studies. Women may be recruited to non-interventional trials such as observational or qualitative studies for delay in labour and to all other trials in pregnancy or the postnatal period.

8 Randomisation

Randomisation will be by telephone via an automated secure system developed by the Health Services Research Unit at Aberdeen University. Eligibility will be confirmed as part of the recruitment process and checked by the automated telephone randomisation system. Although some identifiable data is provided it is insufficient to constitute personal identifiable data.

Randomisation will be available 24 hours a day. Participants will be randomised at the level of the individual in a 1:1 ratio to either standard dose regimen oxytocin or high dose regimen oxytocin. A minimisation algorithm will be used to ensure balance in the allocation over the following variables:

- degree of cervical dilation in cm (<6/>=6);
- age in years (<20/>=20 to <30/>=30 to <40/>=40);
- maternity unit

A 'random element' will be included in the minimisation algorithm so that each patient has a probability (unspecified here) of being randomised to the opposite treatment that they would have otherwise received.

Resupply of subsequent treatments, should they be required, will be by the same secure system to guarantee allocation to the same dose as initial randomisation.

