12.1 Sample size

The sample size is informed by the pilot study¹, recent survey of practice and Cochrane review⁶. The pilot study indicated a CS rate of 32% in the standard dose group (95%CI: 19% to 45%), whilst responses from the survey of practice (n=60 responses) indicate that a 25% relative reduction would be considered an important clinical difference to change practice. Detecting a difference of this size assuming a standard dose group rate of 32% (8% absolute reduction down to 24%) with 90% power (p=0.05) will require 1320 women. If the control group rate is lower, e.g. 24%, recruiting 1500 women would give 80% power to detect the same relative difference. We have selected the latter figure as our target sample size. The independent Data Monitoring Committee (DMC) will review the event rate to monitor the control rate on a six-monthly basis throughout the recruitment period.

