12.2 Statistical analysis

A separate Statistical Analysis Plan will provide a detailed description of the planned analyses. A brief outline is given below.

Point estimates, 95% confidence intervals and p-values from two-sided tests will be calculated for all main outcome measures. Outcome will be adjusted for the minimisation variables. Analysis will be of all randomised subjects in the intention to treat population.

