12.2.4 Subgroup Analyses

Subgroup analyses will be limited to degree of cervical dilation at recruitment (<=6m/>6cm). Tests for statistical heterogeneity will be performed prior to any examination of effect estimates with subgroups. The results of subgroup analyses will be treated with caution and used for the purposes of hypothesis generation only.

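### The one planned effect-modification analysis uses cervical dilation in two groups only; a supplementary interaction in cm would detect and describe a gradual change better

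*Combined protocol and SAP*

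**What the plan says.** Section 6.3 (Secondary objectives) sets the objective: "To explore any variation in effect in women randomised with cervical dilation <6cms and >=6cms". Section 8 (Randomisation) minimises on "degree of cervical dilation in cm (<6/>=6"), so the variable is in cm and is banded for allocation.

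Dilation is assessed in cm at entry, because eligibility depends on it. Section 7.3 states: "Delay is confirmed when progress of <1 cm in 2 hours is found on repeat vaginal examination". Established labour starts from 4 cm (section 7.3) and full dilation at 10 cm is an exclusion (section 7.4), so women enter at about 4 cm to just under 10 cm.

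Section 12.2.4 limits subgroup analysis to this one factor, in two groups, for hypothesis generation only. It adds: "Tests for statistical heterogeneity will be performed prior to any examination of effect estimates with subgroups". Its boundary differs from the other sections: 6 cm falls in the lower group there, and in the upper group in sections 5.2, 6.3 and 8.

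Section 5.2 explains the choice of 6 cm. It cites outside data and a consensus statement that use 6 cm as a marker, and ties the subgroup to the trial's worldwide relevance. Section 12.2 calls itself a brief outline and defers detail to a separate SAP, whose text is not in the document supplied.

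**The concern.** The two groups treat 4 and 5 cm as one state and 6 to 9 cm as another. If the relative effect of the higher dose drifts steadily with dilation, comparing two pooled relative risks discards the ordering within each group. That costs power. It also leaves nothing to distinguish a steady drift from a threshold, because two estimates cannot show a shape. The question matters to the plan's authors: it is the only effect modifier they kept, and section 5.2 relies on it for the trial's relevance outside the UK.

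**Working it through.** **1. The plan's own sample size.** The inputs are "assuming a standard dose group rate of 32% (8% absolute reduction down to 24"%), "with 90% power (p=0.05) will require 1320 women", and "p-values from two-sided tests will be calculated for all main outcome measures". With the pooled-variance formula for two proportions:

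n per arm = [1.960 × √(2 × 0.28 × 0.72) + 1.282 × √(0.32 × 0.68 + 0.24 × 0.76)]² / 0.08² = 659.9, rounded to 660. The total is 1320, as stated.

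The plan also says: "If the control group rate is lower, e.g. 24%, recruiting 1500 women would give 80% power to detect the same relative difference". For 24% v 18% with 750 per arm, the calculation gives 81.5%, which agrees. No power is claimed for the interaction.

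**2. Information kept by the split.** The documents give no distribution of dilation, so one has to be assumed. Take equal numbers at 4, 5, 6, 7, 8 and 9 cm.

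- Variance of cm = 35/12 = 2.917.
- Split <6/≥6: the shares are 1/3 and 2/3, and the group means 4.5 and 7.5 cm (3 cm apart). The squared correlation with cm is (1/3 × 2/3 × 3²) / 2.917 = 0.69, a loss of 31%.
- Split ≤6/>6: the shares are equal, and the means 5 and 8 cm. The squared correlation is (1/2 × 1/2 × 3²) / 2.917 = 0.77, a loss of 23%.

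Over five assumed distributions, the <6/≥6 split loses about 25-45%. The loss reaches 55% in one extreme case: RR 0.4 at 4 cm rising to 1.4 at 9 cm, with 15% of women below 6 cm.

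**3. Power of the interaction test.** Assume 1500 women, equal numbers at each cm, 24% Caesarean section in the standard arm at every dilation, and variances evaluated at RR 0.75 (24% v 18%). Per woman per arm, the variance term is 0.76/0.24 + 0.82/0.18 = 7.722.

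- SE of the slope per cm = √(7.722 / (750 × 2.917)) = 0.0594.
- SE of the two-group contrast (250 and 500 per arm) = √(7.722/250 + 7.722/500) = 0.2153.

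The group means are 3 cm apart, so a slope of b per cm on the log RR gives z = b/0.0594 in cm and z = 3b/0.2153 for the split. Power is Φ(z − 1.96), plus a negligible opposite tail.

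| Assumed truth | z, split | Power, split | z, cm | Power, cm |
|---|---|---|---|---|
| Slope 0.15 per cm, RR 0.75 at 6 cm (0.56 at 4 to 1.18 at 9) | 2.09 | 55% | 2.52 | 71% |
| Slope 0.08 per cm, RR 0.75 at 6 cm (0.64 at 4 to 0.95 at 9) | 1.11 | 20% | 1.35 | 27% |
| Step at 6 cm (RR 0.60 below, 0.95 from 6) | 2.13 | 57% | 1.77 | 42% |

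For the step, log(0.95/0.60) = 0.460 and z for the split is 0.460/0.2153 = 2.13. In cm it is √0.69 × 2.13 = 1.77.

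Over five assumed distributions at a 24% control rate, the ranges (split v cm) are:

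- steeper slope: 36-55% v 60-73%
- milder slope: 14-20% v 22-28%
- step: 36-62% v 20-48%

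**4. What the two-group test can find.** With half the women in each group, SE = √(2 × 7.722/375) = 0.203. At 80% power the detectable ratio of relative risks is exp(−2.80 × 0.203) = 0.57. With 30% or 70% below the cut it is 0.54. At a 32% control rate the corresponding figures are 0.62 and 0.60.

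**5. The boundary.** With equal numbers at each cm, 1/6 of women (250 of 1500) are at exactly 6 cm. They change group between sections 6.3 and 12.2.4.

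**The case against.** The strongest defence is that the split is the question. Section 5.2 takes 6 cm from an outside debate, fixes it in advance and gives its reason. A linear slope answers something else, and under a true step at 6 cm it is the weaker test. Section 12.2.4 deliberately restricts subgroup work, and a second interaction test loosens that restriction. All of this stands, and it is why the two-group analysis should remain the main one.

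Three stronger readings are tempting, and the documents do not support them.

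- **The split is why a gradient would be missed.** Low power comes mainly from sizing the trial on the main effect. The test in cm also misses the milder slope in 72-78% of trials. A steep gradient (RR 0.4 to 1.4) is found by the split in 68-98%.
- **A null test would be taken as proof of no variation.** Section 12.2.4 already asks for caution and hypothesis generation only.
- **The cm value goes unrecorded.** Section 8 names dilation in cm, and the randomisation form is not in the document, so no gap is shown.

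The separate SAP may already contain a continuous analysis. That cannot be judged from the supplied text, but the two-group wording and the limitation in section 12.2.4 do not provide for one.

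**Conclusion.** The point holds as a modest improvement. The only effect-modification analysis described uses a cm measurement in two groups. Against a gradual change, this loses about 25-45% of the information on a linear trend and leaves the shape undescribed. In the assumed scenarios at a 24% control rate, the test in cm has higher power for either slope and lower power for a step at 6 cm. The documents do not say which shape is true, so neither analysis replaces the other.

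The distribution of dilation, the gradients and a control rate constant across dilation are all assumptions, and the percentages move with them. The boundary mismatch rests on no assumption and has to be reconciled in any case. The primary analysis and the sample size are unaffected.

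**What to change.** In section 12.2.4:

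- Keep the pre-specified two-group analysis as the main subgroup analysis.
- State one boundary, consistent with sections 5.2, 6.3 and 8, so that women at exactly 6 cm belong to one defined group.
- Add one pre-specified supplementary analysis: a treatment-by-dilation interaction (cm, linear, 1 df) in the same regression model, with dilation in cm as its main effect. Report fitted relative risks and 95% confidence intervals at a few values, for example 4, 6 and 8 cm.
- Label the supplementary analysis hypothesis-generating, as the section already does for the split.

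The cost is one more model and one table or figure. The downside is a second exploratory p-value on the same variable. Naming the two-group test as the main one in advance prevents a choice between the two after the results are seen.
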